1.1 Nonclinical Data

As the QW formulation to be administered in this trial contains brexpiprazole fumarate as the active pharmaceutical ingredient, repeated-dose oral toxicity studies in rats and monkeys and in vitro and in vivo genotoxicity studies have been conducted.

A 4-week repeated-dose oral toxicity study of brexpiprazole fumarate was conducted in rats. Changes in general condition attributable to the pharmacological action of the drug included abnormal posture in males and females at doses of 30 mg/kg/day and higher, lacrimation in females at 30 and 100 mg/kg/day, hypothermia, tremor, and lacrimation in males at 100 and 300 mg/kg/day, and incomplete eyelid closure in females at doses of 10 mg/kg/day and higher. Suppressed body weight gain associated with decreased food consumption was observed in males at doses of 30 mg/kg/day and higher and in females at 100 mg/kg/day. Decreased body temperature was observed in both sexes at doses of 30 mg/kg/day and higher. Lobular hyperplasia and milk secretion in the mammary glands in females at doses of 30 mg/kg/day and higher were considered to be due to D₂

antagonism and the resulting increase in serum prolactin levels.⁸ In addition, mucification of the vagina at 3 mg/kg/day and higher and of the uterine cervix at 10 mg/kg/day and higher were considered to be due to activation of luteal function triggered by the increase in serum prolactin. Brain lesions observed in males at 300 mg/kg/day and in females at 100 mg/kg/day were associated with a marked decrease in body temperature, as seen in previous toxicity studies of brexpiprazole. In males, histopathological lesions in the testis, epididymis, and seminal vesicles were observed at 100 and 300 mg/kg/day. In conclusion, the no observed adverse effect level (NOAEL) was determined to be 30 mg/kg/day for males and 10 mg/kg/day for females under the conditions of the study.

A 4-week repeated-dose oral toxicity study of brexpiprazole fumarate was conducted in monkeys. Clinical signs included tremors in males and females at 3 and 10 mg/kg/day. Drowsiness, crouching, and eyelid closure were observed in males and females at 10 mg/kg/day, and drowsiness was also observed in males at 3 mg/kg/day. Decreased mean blood pressure was observed in both sexes at doses of 3 mg/kg/day and higher and decreased body temperature was observed in both sexes at 10 mg/kg/day. QT corrected for heart rate (QTc) was prolonged in males at 10 mg/kg/day, but only on Day 1. The NOAEL was considered to be 1 mg/kg/day for both males and females under the conditions of the study.

In 4-week repeated-dose oral toxicity studies in rats and monkeys, the effects of brexpiprazole fumarate were similar to those seen in clinical studies of brexpiprazole. No new or unexpected systemic toxicities were observed with brexpiprazole fumarate compared to brexpiprazole.^{9,10,11,12,13,14,15} There was also no apparent difference in the toxicokinetic profile between brexpiprazole and brexpiprazole fumarate in both rats and monkeys.

Brexpiprazole fumarate was not genotoxic in a bacterial reverse mutation test, a bonemarrow micronucleus test in rats, or an unscheduled DNA synthesis test in rats.

All relevant data from nonclinical studies in animals (including PK and toxicity studies) are presented in the Investigator's Brochure (IB).

1.2 Clinical Data

1.2.1 Clinical Pharmacology Trial for Comparative Investigation of the Pharmacokinetics, Tolerability, and Safety of Three Types of QW Formulation Administered as Single Oral Doses in Patients With Schizophrenia (Japan 331-102-00021)

A multi-center, open-label, clinical pharmacology trial for comparative investigation of the PK, tolerability, and safety following single oral administration of one of three types

of brexpiprazole QW formulation (Table 1.2-1) in patients with a diagnosis of schizophrenia (295.90) based on the Diagnostic and Statistical Manual of Mental Disorders, Fifth edition (DSM-5[®]).

Subjects received one brexpiprazole 2 mg conventional tablet and, after a washout period, received a single administration of one of three QW formulations (12 mg of brexpiprazole).

Table 1.2-1Three QW Formulations Used in Trial 331-102-00021				
Candidate Formulation	No. of Subjects	Bulk Form	Release Control System	
QW-A formulation	6	Fumarate	OROS	
QW-B formulation	6	Fumarate	HG matrix tablet	
QW-C formulation	8	Amorphous solid dispersion	HG matrix tablet	

The incidence of adverse events (AEs) at 12 mg of brexpiprazole was 33.3% (2/6) in the QW-A formulation group, 33.3% (2/6) in the QW-B formulation group, and 12.5% (1/8) in the QW-C formulation group. No AEs occurred in more than 1 subject in any formulation group. In addition, no serious adverse events (SAEs), severe AEs, or AEs leading to trial discontinuation were reported in any formulation group.

All QW formulations were associated with extended median t_{max} as compared with the conventional tablet, indicating controlled release of the drug from all QW formulations. The mean $t_{1/2,z}$ after dosing of each QW formulation was similar to that after dosing of the conventional tablet. The main PK parameters of each QW formulation are shown in Table 1.2-2.

Table 1.2-2Main Pharmacokinetic Parameters of Each QW Formulation in Trial 331-102-00021					
Candidate Formulation (mg)	No. of Subjects	C _{max} (ng/mL)	AUC∞ (h•ng/mL)	t _{max} ^a (h)	t1/2,z (h)
QW-A formulation	6	61.11	6840	30.13	71.5
(12 mg)		(39.75)	(5360)	(23.25 - 49.57)	(18.2)
QW-B formulation	6	46.67	4210	24.60	68.4
(12 mg)		(16.75)	(1260)	(23.30 - 25.58)	(26.3)
QW-C formulation	8	63.56	7780	18.09	90.2
(12 mg)		(23.26)	(6170)	(8.60 - 48.00)	(53.9)

Mean (standard deviation)

^aMedian (minimum - maximum)

1.2.2 Clinical Data of Conventional Tablet of Brexpiprazole

Among clinical trials of the conventional tablet, the results of trials that confirmed safety and tolerability at the maximum dose of 12 mg and the results of trials in Japanese patients with schizophrenia are summarized below. Refer to the IB for further information.

1.2.2.1 Phase 1 Multiple-dose Trial in Subjects With Schizophrenia or Schizoaffective Disorder (US 331-08-205)

A total of 48 subjects with schizophrenia or schizoaffective disorder received multiple doses of oral brexpiprazole at 2, 4, 6, 8, 10, or 12 mg (6 subjects per dose group plus 2 subjects per group given brexpiprazole 1 mg as a reference group) for 14 days.

The C_{max} and AUC_{0-24h} increased dose-dependently after multiple-dose administration of brexpiprazole (1 to 12 mg). The $t_{1/2,z}$ of brexpiprazole at steady state ranged from 81.14 to 106.83 hours.

The incidence of adverse events (AEs) in subjects receiving the investigational medicinal product (IMP) (including subjects in the 1-mg reference group) was 89.6% (43/48). Adverse events reported in more than 1 subject included anxiety (31.3%, 15/48), insomnia (22.9%, 11/48), constipation, headache (14.6%, 7/48 each), stomach discomfort, pain in extremity (10.4%, 5/48 each), dyspepsia, agitation, nasal congestion (8.3%, 4/48 each), back pain, sedation, oropharyngeal pain (6.3%, 3/48 each), tachycardia, tongue disorder, upper respiratory tract infection, blood pressure decreased, arthralgia, akathisia, dizziness, and hypotension (4.2%, 2/48 each). Of those, AEs reported in more than 1 subject and considered to be related to the IMP were anxiety (16.7%, 8/48), insomnia, constipation, stomach discomfort (8.3%, 4/48 each), sedation (6.3%, 3/48), tongue disorder, blood pressure decreased, akathisia, and headache (4.2%, 2/48 each). Serious adverse events (SAEs) reported in the 12-mg group were drug hypersensitivity and anxiety in 1 subject each and both events resolved on the day after onset. In addition, no AEs in the 12-mg group led to discontinuation, demonstrating good tolerability of brexpiprazole at up to 12 mg.

1.2.2.2 QT/QTc Trial in Subjects With Schizophrenia or Schizoaffective Disorder (US 331-10-242)

A total of 205 subjects with schizophrenia or schizoaffective disorder received multiple doses of brexpiprazole at 4 mg or 12 mg or placebo for 11 days or moxifloxacin once daily for one day. The 12-mg group included 67 subjects.

The primary endpoint was the time-matched QTcI change from baseline corrected for placebo on Day 11 of brexpiprazole treatment. The results demonstrated that there was no QTcI prolongation after brexpiprazole treatment at either 4 or 12 mg.

The incidence of AEs in subjects receiving 12 mg of brexpiprazole was 71.6% (48/67). Adverse events reported in more than 1 subject included dizziness (8 subjects, 11.9%), akathisia, extrapyramidal disorder, restlessness, headache, nausea (5 subjects each, 7.5%), constipation, somnolence, insomnia (4 subjects each, 6.0%), orthostatic hypotension, vomiting, sedation (3 subjects each, 4.5%), stomach discomfort, nasopharyngitis, muscle rigidity, drooling, application site pruritus, vision blurred, salivary hypersecretion, anaemia, and diarrhoea (2 subjects each, 3.0%). Of those, AEs reported in more than 1 subject and considered to be related to the IMP were dizziness (10.4%, 7/67), extrapyramidal disorder (7.5%, 5/67), akathisia, headache (6.0%, 4/67 each), nausea, sedation, somnolence (4.5%, 3/67 each), constipation, salivary hypersecretion, vomiting, muscle rigidity, drooling, and orthostatic hypotension (3.0%, 2/67 each). No SAEs were reported in the 12-mg group. Adverse events leading to discontinuation in the 12-mg group were dizziness (1.5%, 1/67 each). The trial results demonstrated good tolerability of brexpiprazole at 12 mg.

1.2.2.3 Phase 1 Multiple-dose Trial in Subjects With Schizophrenia (Japan 331-10-001)

A total of 21 subjects with schizophrenia received multiple doses of brexpiprazole at 1, 4, or 6 mg once daily for 14 days.

Overall, 90.5% of subjects (19/21) experienced AEs. The incidence of AEs by treatment group was 71.4% (5/7) in the 1-mg group, 100.0% (8/8) in the 4-mg group, and 100.0% (6/6) in the 6-mg group. The most frequently reported AEs (incidence \geq 5% of all subjects) were blood prolactin increased (38.1%, 8/21), blood creatine phosphokinase increased (14.3%, 3/21), nausea, nasopharyngitis, blood pressure increased, blood prolactin decreased, insomnia, and schizophrenia (9.5%, 2/21 each). The majority of events, including blood prolactin increased, were considered potentially related to the IMP. Serious adverse events of schizophrenia were reported in 2 subjects (1 each in the 1-mg and 4-mg groups), both of which led to discontinuation.

The trial results demonstrated the safety and tolerability of brexpiprazole at up to 6 mg in Japanese subjects with schizophrenia.

1.2.2.5 Long-term Trial in Subjects With Schizophrenia (Japan 331-10-003)

This long-term trial conducted in Japan was an open-label trial to evaluate the safety and efficacy of long-term administration of brexpiprazole in subjects with schizophrenia, either continuing treatment from the dose-finding trial 331-10-002 (rollover subjects) or newly enrolled in this trial.

All efficacy endpoints, including PANSS total score and Clinical Global Impression-Severity of Illness (CGI-S) score, remained stable until Week 52.

The incidence of AEs was 85.2% in newly enrolled subjects, 80.6% in rollover subjects, and 83.6% in all subjects. The most frequently reported AE was nasopharyngitis (25.1%) in newly enrolled subjects, schizophrenia (26.5%) in rollover subjects, and nasopharyngitis (23.1%) in all subjects. Most AEs were mild or moderate in severity. No deaths were reported in this trial. The incidence of SAEs was 10.4% in newly enrolled subjects, 18.4% in rollover subjects, and 13.2% in all subjects. Serious adverse events reported in more than 1 subject were schizophrenia in newly enrolled and rollover subjects and dehydration, akathisia, and schizophrenia in all subjects. The incidence of AEs leading to discontinuation was 10.9% in newly enrolled subjects, 23.5% in rollover subjects, and 15.3% in all subjects. The most frequently reported AE leading to discontinuation was schizophrenia in newly enrolled subjects, rollover subjects, and all subjects. No clinically meaningful changes were noted in laboratory test values, vital signs, or ECGs in newly enrolled subjects, rollover subjects, or all subjects. The mean change in weight from Period 2 baseline to the final assessment (last observation carried forward [LOCF]) was 0.34 kg in newly enrolled subjects, 2.02 kg in rollover subjects, and 0.93 kg in all subjects. There was no marked difference in safety results between newly enrolled subjects and rollover subjects, indicating that switchover to brexpiprazole monotherapy from prior treatment with existing antipsychotic drugs has no significant impact on safety.

1.3 Pharmacokinetics

A simulation was performed using plasma brexpiprazole concentrations observed after dosing of the QW-A formulation at 12 mg in Japanese Trial 331-102-00021 to estimate steady-state plasma brexpiprazole concentrations for the QW-A formulation at 24 and 48 mg. The estimated PK parameters are shown in Table 1.3-1.

Results from Japanese and non-Japanese clinical trials showing PK parameters of repeated administration of brexpiprazole at the clinically recommended doses (Japan: 2 mg; US: 2 and 4 mg) and the maximum dose of 12 mg at which safety and tolerability has been confirmed are summarized in Table 1.3-2.

The PK of brexpiprazole was similar between Japanese and non-Japanese in healthy adults receiving a single dose of brexpiprazole at 0.2 to 6 mg (US 331-07-201 and Japan 331-07-002) and in subjects with schizophrenia receiving multiple doses of brexpiprazole at 1, 4, and 6 mg (US 331-08-205 and Japan 331-10-001). A non-Japanese population PK analysis (Trial 331-12-208) did not identify race as a variation factor for the PK of brexpiprazole.

Table 1.3-1Estimated Pharmacokinetic Parameters of Brexpiprazole QWFormulation at Steady State Based on Simulation				
Summary	PK Parameter	24 mg	48 mg	
A simulation was performed with a PK model created based on PK data on the QW-A formulation (n = 6) from Trial 331-102-00021 (Japan).	C _{ss,max} (ng/mL)	88 (69.3)	176 (139)	
	C _{ss,min} (ng/mL)	27.6 (27.8)	55.1 (55.6)	
	AUC168h (ng·h/mL)	9450 (7890)	18900 (15800)	

C_{ss},max = Maximum plasma concentration at steady state

C_{ss},min = Minimum plasma concentration at steady state Mean (standard deviation)

Table 1.3-2	Pharmacokii State	netic Parameters o	of Brexpiprazole at	Steady
Trial No. No. of Subjects	PK Parameter	2 mg	4 mg	12 mg
331-10-001 (Japan) 4 mg (N = 7)	C _{max} (ng/mL)	ND	164.63 (101.96)	ND
	AUC24h (ng·h/mL)	ND	3238 (2184)	ND
	$\begin{array}{c} AUC_{24h} \times 7^{a} \\ (ng \cdot h/mL) \end{array}$	ND	22666	ND
331-08-205 (US) 2 mg (N = 6) 4 mg (N = 5) 12 mg (N = 4)	C _{ss,max} (ng/mL)	81.2 (28.3)	199 (134)	382 (30.3)
	C _{ss,min} (ng/mL)	56.8 (23.0)	112 (75.3)	205 (51.7)
	AUC24h (ng·h/mL)	1620 (594)	3950 (2860)	6950 (797)
	$\begin{array}{c} AUC_{24h} \times 7^{a} \\ (ng \cdot h/mL) \end{array}$	11340	27650	48650
331-10-242 (US) 4 mg (N = 64) 12 mg (N = 53)	C _{max} (ng/mL)	ND	170 (69.8)	462 (249)
	Css, min (ng/mL)	ND	102 (55.2)	305 (192)
	$\begin{array}{c} AUC_{\tau} \\ (ng \cdot h/mL) \end{array}$	ND	3100 (1400)	8880 (5110)
	$\begin{array}{c} AUC_{\tau} \times 7^{a} \\ (ng \cdot h/mL) \end{array}$	ND	21700	61260

C_{ss},max = Maximum plasma concentration at steady state

C_{ss},min = Minimum plasma concentration at steady state

Mean (standard deviation)

ND = No data

^a7-day data of AUC (7 times the mean AUC_{24h} for each dosing interval)

1.4 Known and Potential Risks and Benefits

Data from overseas phase 1 trials of the conventional tablet of brexpiprazole demonstrate safety and good tolerability in healthy adults exposed to single doses of 0.2 to 6 mg and multiple doses of 2 mg/day.^{16,17,18} Data from completed US multiple-dose trials show favorable tolerability in patients with schizophrenia or schizoaffective disorder exposed to multiple doses of up to 12 mg/day of brexpiprazole,¹⁹ in patients with MDD exposed to 4 mg/day of brexpiprazole with commercially available antidepressants, 20,21 and in patients with attention deficit hyperactivity disorder (ADHD) exposed to up to 4 mg/day of brexpiprazole with commercially available stimulants. Furthermore, data from Japanese phase 1 trials indicate favorable tolerability in healthy adults exposed to single doses of up to 4 mg/day^{22} and in patients with schizophrenia exposed to multiple doses of up to 6 mg/day.²³ In a Japanese dose-finding trial (331-10-002) in subjects with schizophrenia, the primary endpoint of change from baseline at Week 6 in PANSS total score in the 2 mg brexpiprazole group was significantly different from that in the placebo group. The change observed in the 4 mg group was numerically larger than that in the placebo group, though the difference was not significant. Brexpiprazole was well tolerated in subjects at doses of 1, 2, and 4 mg/day.²⁴

Data from completed clinical trials at present indicate that the maximum tolerated dose (MTD) of brexpiprazole for healthy adults is 6 mg as single-dose administration and 2 mg as once-daily, multiple-dose administration (14 days). The MTD of brexpiprazole in patients with schizophrenia, MDD, agitation associated with Alzheimer-type dementia, and ADHD has not been established. Data from completed phase 1 multiple-dose trials indicate tolerability of brexpiprazole at multiple oral doses up to 12 mg/day in patients with schizophrenia or schizoaffective disorder, up to 4 mg/day when administered as an adjunctive therapy in adult patients with MDD or ADHD, and up to 3 mg/day when administered as an adjunctive therapy in elderly patients (70 to 85 years of age) with MDD.

See the IB for further information on brexpiprazole and adverse drug reactions.

2 Trial Rationale and Objectives

2.1 Trial Rationale

As described in Section 1 Introduction, maintenance of drug compliance is thought to be instrumental in alleviating symptoms and achieving favorable outcomes in the treatment

of schizophrenia; however, in comparison with other chronic diseases, schizophrenia is generally associated with poor drug adherence due mainly to lack of consciousness of disease and cognitive impairment. Long-acting drugs have been introduced into clinical practice as a measure to improve patient adherence to medication, but currently the only commercially available long-acting antipsychotics are all injectable formulations, thus reflecting an unmet medical need for more easy-to-use long-acting antipsychotics.

Brexpiprazole, a once-daily oral formulation, has demonstrated efficacy and safety in the treatment of schizophrenia in clinical trials in subjects with schizophrenia conducted in Japan, the US, and Europe and is approved in Japan and overseas as a treatment for schizophrenia. Otsuka is now developing a QW formulation, utilizing the same less invasive route of administration as conventional brexpiprazole, namely the oral route, but with a different formulation to enable reduced dosing frequency.

In order to find the most appropriate QW formulation, we conducted a clinical pharmacology trial (Japan 331-102-00021) in Japan for comparative investigation of the PK, tolerability, and safety of 3 types of brexpiprazole QW formulation administered as single oral doses in patients with schizophrenia.

Given that the approved clinical dose of brexpiprazole for schizophrenia in Japan is 2 mg and that the dose found to be safe in Japanese subjects in a dose-finding trial (Japan 331-10-002) and a long-term trial (Japan 331-10-003) is 4 mg, the target PK profile of the QW formulation in repeated administration should ideally be as follows: the trough concentration should not fall below that for the brexpiprazole 2 mg conventional tablet and the peak concentration should not significantly exceed that for the brexpiprazole 4 mg conventional tablet.

Data from single 12-mg doses of each QW formulation in Trial 331-102-00021 (Japan) were used to estimate plasma brexpiprazole concentrations following repeated administration. The results indicate that only the QW-A formulation is likely to attain the target PK profile.

Furthermore, a simulation was performed, using a model created based on the PK results for the 12 mg QW-A formulation, to find the dose of the QW formulation that would achieve the target PK profile at the steady state. The results suggest that plasma brexpiprazole concentrations after administration of the QW formulation at 48 mg will generally remain within the target PK profile and will not significantly exceed the peak concentration at the steady state observed after administration of the conventional tablet at 4 mg.
With the above taken into consideration, in this trial, we have decided to use the QW-A formulation with OROS to evaluate the PK, tolerability, and safety of the brexpiprazole QW formulation following single and repeated oral administration in patients with schizophrenia.

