A clinical pharmacology trial for comparative investigation of the PK, tolerability, and safety of 3 types of brexpiprazole QW formulation administered as single oral doses in patients with schizophrenia (Japan 331-102-00021) has demonstrated the safety and tolerability of a single 12-mg dose of the QW formulation. The results of a simulation of repeated administration of the QW formulation at 48 mg based on the PK results of Trial 331-102-00021 indicate that plasma brexpiprazole concentrations after repeated administration of the QW formulation at 48 mg will remain roughly between the trough concentration after administration of the brexpiprazole 2 mg conventional tablet and the peak concentration after administration of the 4 mg conventional tablet, thus suggesting that plasma brexpiprazole concentrations after repeated administration of the QW formulation at 48 mg will not greatly exceed the steady-state peak concentration of the 4 mg conventional tablet, the dose at which safety has been confirmed in Japanese patients. Furthermore, the mean steady-state C_{max} at the maximum dose of 12 mg at which safety and tolerability was confirmed in an overseas repeated administration trial (331-08-205) and an overseas QT/QTc trial (331-10-242) of brexpiprazole conventional tablets in subjects with schizophrenia and schizoaffective disorder was 382 and 462 ng/mL, respectively, and the estimated mean steady-state C_{max} after repeated administration of brexpiprazole QW formulation at 48 mg (176 ng/mL) was lower than either of these results. In view of these findings, the dose was set at 48 mg for the QW formulation to be used in the single administration period (Cohort 1). However, since there is no clinical experience of administering either the brexpiprazole OW formulation or the conventional tablet at doses higher than 12 mg, subjects will be first given the QW formulation at a dose of 24 mg and only subjects for whom safety and tolerability has been confirmed will then receive the drug at 48 mg. For the conventional tablet, the dose was set at 2 mg, the recommended dose for schizophrenia.

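### Tables 1.2-2 and 1.3-1 disagree without explanation: the simulated 48 mg steady-state exposure is about 30% below the dose-scaled 12 mg single-dose data on which it is built

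*Protocol*

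**What the plan says.** Table 1.2-2 (Section 1.2.1) reports the earlier single-dose trial at 12 mg. Its QW-A row reads "QW-A formulation 6 61.11 6840 30.13 71.5": six subjects, mean Cmax in ng/mL, mean AUC∞ in h·ng/mL, median tmax in hours and mean half-life in hours. The standard deviations are 39.75 for Cmax, 5360 for AUC∞ and 18.2 for half-life.

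Table 1.3-1 (Section 1.3) gives simulated steady-state values, also as mean (SD). It names its source: "A simulation was performed with a PK model created based on PK data on the QW-A formulation (n = 6) from Trial 331-102-00021 (Japan". For 24 and 48 mg, the peak row reads "88 (69.3) 176 (139", the trough row "27.6 (27.8) 55.1 (55.6" and the weekly AUC row "9450 (7890) 18900 (15800" (closing brackets cut off).

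Table 1.3-2 gives mean steady-state peaks for the 4 mg tablet of 164.63, 199 and 170 ng/mL in three trials.

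Section 2.1 sets the target profile: a trough not below that of the 2 mg tablet and a peak not much above that of the 4 mg tablet. It concludes that concentrations at 48 mg "will not significantly exceed the peak concentration at the steady state observed after administration of the conventional tablet at 4 mg". Section 2.3.2.1.1 repeats this. It adds a comparison with the 12 mg tablet peaks of 382 and 462 ng/mL, noting that the estimate for the "brexpiprazole QW formulation at 48 mg (176 ng/mL) was lower than either of these results".

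Sections 2.3.2.1.2 and 3.8.1 provide for a new simulation from Cohort 1 data before Cohort 2 starts.

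**The concern.** A linear simulation built on six subjects should return something close to what those subjects showed. Here the simulated steady-state peak at 48 mg is lower than a single 48 mg dose would give if the observed 12 mg mean were scaled up. Repeated dosing can only add to a single-dose profile, so the two tables cannot both describe the same mean subject under linear kinetics.

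Two things are at stake. First, the stated reason for expecting 48 mg to sit near the 4 mg tablet peak uses the lower set of figures and does not mention the other. Second, Section 3.8.1 relies on simulation again to judge 48 mg against the target limits. Neither document specifies the model or requires a check that it reproduces the observed single-dose data before its steady-state output is used.

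**Working it through.** **Inputs.** Table 1.2-2, QW-A 12 mg: Cmax 61.11 (SD 39.75), AUC∞ 6840 (SD 5360), tmax 30.13 h, half-life 71.5 h (SD 18.2), n = 6. Table 1.3-1 and Table 1.3-2 values as above. Dosing interval 168 h.

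**Step 1: is the simulation linear in dose?** From 24 to 48 mg the ratios are 176/88 = 2.00, 55.1/27.6 = 2.00 and 18900/9450 = 2.00. Yes.

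**Step 2: can 176 and 18900 be reproduced from the 12 mg data?** Under linear kinetics, in each subject and so in the mean, the steady-state peak is at least the single-dose peak, and AUC over one interval at steady state equals single-dose AUC∞ at the same dose.

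| Quantity | Observed 12 mg, scaled | Simulated | Ratio |
|---|---|---|---|
| Peak, 48 mg | 4 × 61.11 = 244.4 (single dose) | 176 (steady state) | 0.72 |
| AUC, 48 mg | 4 × 6840 = 27360 | 18900 | 0.69 |
| Peak, 24 mg | 2 × 61.11 = 122.2 | 88 | 0.72 |
| AUC, 24 mg | 2 × 6840 = 13680 | 9450 | 0.69 |

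They cannot. Scaled back to 12 mg, the simulation implies a steady-state peak of 176/4 = 44.0 and an AUC of 18900/4 = 4725, both below what one dose produced.

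**Step 3: is the single-dose row coherent in itself?** With k = ln 2/71.5 and zero-order release over 30.13 h, Cmax = (6840/30.13) × (1 − e^(−30.13k)) = 57.5, close to the observed 61.11. In the same one-compartment model, a 48 mg steady-state peak of 176 would need a 12 mg AUC∞ of about 4207, against 6840 observed.

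**Step 4: rough steady-state peak at 48 mg.** The accumulation factor is 1/(1 − e^(−168k)) = 1.244.
- Observed peak, scaled: 244.4 × 1.244 = 304 ng/mL.
- One-compartment peak, scaled: 4 × 57.5 × 1.244 = 286 ng/mL.
- Half-life one SD either side (53.3 to 89.7 h): 275 to 336 by the first route and 332 to 259 by the second, so about 260 to 336 overall.

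The trough is less informative. The one-compartment value is 75 ng/mL at 71.5 h but runs from 55 to 89 over the same half-life range, so it reaches the simulated 55.1 at one end.

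**Step 5: ratio to the 4 mg tablet peaks (199, 170, 164.63).**
- 176: 0.88, 1.04, 1.07.
- 244.4, before accumulation: 1.23, 1.44, 1.48.
- 304: 1.53, 1.79, 1.85.

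**Step 6: simple explanations.**
- *Geometric means.* If the data are lognormal (an assumption), the geometric mean is mean/√(1 + CV²). Scaled fourfold this gives about 205 for Cmax and 21500 for AUC∞, still above the simulated arithmetic means of 176 and 18900.
- *Sampling error.* The 95% interval for the scaled mean Cmax is 4 × (61.11 ± 2.571 × 39.75/√6), about 78 to 411 ng/mL. It includes 176.

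**The case against.** The strongest reply is that a simulated population mean need not equal the arithmetic mean of six subjects with CVs of 65% (Cmax) and 78% (AUC∞). A fitted model may pull in an extreme subject, or the simulated population may differ from the six. That is possible, and it is why the mismatch cannot be called an error in the model. But the documents state neither explanation. The simulated CVs (139/176 = 79% for the peak, 15800/18900 = 84% for AUC) are larger than the observed ones, which does not suggest damped variability, though it does not rule it out.

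Second, the wording of Sections 2.1 and 2.3.2.1.1 is hedged, and how far above the 4 mg peak counts as significant is never quantified. A value of 244 lies within one SD of two of the three 4 mg means (upper one-SD limits 267, 333 and 240). This stands: the statements are unsupported by the 12 mg data as tabulated, which is weaker than being shown false.

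Third, Table 1.3-1 does not select the Cohort 2 regimen. Section 3.8.1 calls for a new simulation from Cohort 1, which targets 20 completers with sampling to 312 h at 48 mg, so no fourfold extrapolation from six subjects remains. This also stands and limits the consequence. A reader might infer that the contingency plan looks only upward, to 54 or 60 mg. It does not: Sections 3.8.1 and 3.8.2 also provide 36 and 42 mg if the simulated peak far exceeds that of the 4 mg tablet.

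Fourth, the comparison with the 12 mg tablet survives. Even 336 ng/mL is below 382 and 462.

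**Conclusion.** The two tables are inconsistent, and the protocol does not say why. The simulated 48 mg peak is 28% below, and the simulated weekly AUC 31% below, what the observed 12 mg means imply. The AUC comparison is the firmer of the two, because it does not depend on half-life, sampling times or accumulation. On the tabulated 12 mg data, the statements that 48 mg will not significantly or greatly exceed the 4 mg tablet peak are not supported.

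This rests on dose proportionality from 12 to 48 mg. That is an assumption about the product, but it is also what Table 1.3-1 displays. The 260 to 336 ng/mL range is rough: it combines mean Cmax or AUC∞, mean half-life and median tmax under a simple decline.

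A reader might go further and conclude that the model is wrong, that 48 mg will exceed the 4 mg peak, or that the Cohort 2 simulation will also run 30% low. The documents support none of these. The model and its diagnostics are not shown, the interval from six subjects spans all three 4 mg means, and the later simulation uses different and fuller data. The point calls for correction and explanation of the rationale. It is not a reason to reject the design.

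**What to change.** - Reconcile Tables 1.2-2 and 1.3-1. State the model, the simulated population and the summary statistic, and show the model's predicted 12 mg single-dose Cmax and AUC∞ beside the observed 61.11 and 6840.
- Correct Table 1.3-1 or explain the difference, and restate the sentences in Sections 2.1 and 2.3.2.1.1 to match.
- In Section 3.8.1, require a check that the model reproduces the observed Cohort 1 single-dose Cmax and AUC∞ before its steady-state values are compared with the target limits. Report superposition of the observed Period 3 profiles alongside.

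Appendix 6 records that Amendment 3 responded to Cohort 1 results, so the data for this check already existed. If the Cohort 2 decision has been taken, the same comparison can be added to its record.

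The cost is a few hours of modelling and a wording amendment, with no extra subjects or samples. The downside is that the stated exposures may become less favourable. No dose is proposed here.
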